8.1.1 Sample size

With the high titre RV3-BB neonatal vaccine schedule as the active control arm, the sample size is calculated to demonstrate the non-inferiority of the lower titre vaccine arms with respect to the proportion of participants who have a serum IgA response, 4 weeks after 3 doses of vaccine. A non-inferiority margin of 20% for the difference between arms will be used.

The primary analysis is based on the per protocol population defined as participants who receive all 3 doses of RV3-BB and have no major protocol violations. Thirty percent of participants are expected to be excluded from the PP population due to death, study withdrawal, loss to follow-up, or study non-compliance. Among those in the PP population, a 50% response probability is assumed for the active controls. Based on a one-sided 0.025 level score test with 90% power under the alternative of no difference in response probabilities, 172 participants per arm are required for a total sample size of 688 participants.

8.1.2 *Multicentre studies*

Approximately 688 babies will be randomised across three sites in Malawi. Study visits will be conducted at the sites or at participant homes.

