The difference between high and low titre arms in the response rate and its 95% confidence interval will be calculated. The cumulative probability of anti-rotavirus serum IgA response (as defined above) by 18 weeks of age will be estimated by the Kaplan-Meier method for each vaccine arm. PROC LIFETEST (SAS[®] Version 9.4 or above) will

be used to analyse the response rates (non-responder *vs.* responder). With the CENSOR variable, 1 is commonly used to indicate that an event occurred (subject is a responder) and 0 indicates that the event did not occur (the subject was censored/is a non-responder).

Non-inferiority of the lower titre vaccine will be demonstrated if the upper bound of the confidence interval is below 20%.

Additionally, we will calculate the 95% CI of the difference between vaccine groups in the serum IgA response rate after dose 3 using the method of Newcombe-Wilson without continuity correction for the difference between binomial proportions as implemented in PROC FREQ (SAS® Version 9.4 or above).

Generalized estimating equations (GEE) will be used to analyse the response rates (non-responder vs. responder) after dose 3 using PROC GEE (SAS® Version 9.4 or above). We will calculate a binary outcome ($1 = \ge 3$ -fold increase, 0 = < 3-fold increase from baseline) after dose 1, 2, and 3 for each participant who received vaccine according to the neonatal schedule. After that, we will fit a model with dose as a discrete/categorical/factor variable, vaccine group (low, medium, high dose) as a discrete variable, and dose by vaccine group interaction term. The model will use the binomial distribution for the outcome variable and the exchangeable correlation matrix to account for the correlation between a participant who received vaccine according to the neonatal schedule outcomes. Model will be used for the analysis. Once the model is fit, contrast statements will be used in PROC GENMOD (SAS® Version 9.4 or above) to calculate the difference in the response rate after dose 3 for the high versus low dose and so forth.

In the table, (Estimate, standard error, 95% CI) will be presented.

The general linear model to be fit by GEE is

 $logit(p_{ij}) = \beta_{ij}$

where p_{ij} is the response rate after the i-th dose in the j-th vaccine group. Differences between the β s represent the log odds ratio in response rates.

MCRI-RV3-BB-004

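### The SAP promises a response-rate difference from the GEE but specifies contrasts that are log odds ratios, which cannot be set against the 20-point margin; the main non-inferiority decision does not depend on it

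*SAP*

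**What the plan says.** SAP 8.1.1 sets the margin on the difference scale: "A non-inferiority margin of 20% for the difference between arms will be used". SAP 9.1.2, under its heading on non-inferiority of the lower titres, describes three analyses.

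- **Kaplan-Meier.** The cumulative probability of response by 18 weeks is estimated in each arm. The decision rule follows directly: "Non-inferiority of the lower titre vaccine will be demonstrated if the upper bound of the confidence interval is below 20" per cent.
- **Newcombe-Wilson.** This gives a 95% interval for the difference in response proportions after dose 3. It is introduced as an additional calculation.
- **GEE.** A binary response after each of doses 1, 2 and 3 is modelled with dose, titre group and their interaction. "The model will use the binomial distribution for the outcome variable and the exchangeable correlation matrix". Contrasts are then to be used "to calculate the difference in the response rate after dose 3 for the high versus low dose", and likewise for the other comparison.

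The same section writes the GEE as logit(p_ij) = β_ij, "where p_{ij} is the response rate after the i-th dose in the j-th vaccine group". It adds: "Differences between the β s represent the log odds ratio in response rates". On reporting it says only: "In the table, (Estimate, standard error, 95% CI) will be presented". SAP 9.1.2 carries the same approach over to cumulative vaccine take and its components.

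**The concern.** A contrast of the βs cannot be both a difference in response rates and a log odds ratio. SAP 9.1.2 promises the first and defines the second. It states no identity link, inverse-link step or delta method, and neither document gives a margin on the odds-ratio scale. A programmer who follows the model statement literally would tabulate log odds ratios in a section about non-inferiority, where the only yardstick is 20 points on the difference between arms.

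What is at stake is whether this analysis can be read beside the other two. A log odds ratio with its interval neither supports nor contradicts non-inferiority on the stated margin unless it is converted. Because the approach is reused for vaccine take and its components, the gap recurs there.

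**Working it through.** **Inputs from the documents.** Margin of 20 points on the difference (SAP 8.1.1; Protocol 13.1). Control response 50% (same sections). 172 per arm with 30% expected to leave the per-protocol set, so 172 × 0.70 = 120.4, about 120 evaluable per arm. Model logit(p_ij) = β_ij (SAP 9.1.2). The plan gives no log-odds figure to reproduce, so the check starts from its own margin at its own control rate.

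**Step 1: the margin on the log-odds scale.** For control rate p and lower-titre rate p − 0.20, log OR = ln{[p/(1−p)] / [(p−0.20)/(1.20−p)]}. At p = 0.50 this is ln[(0.5/0.5)/(0.3/0.7)] = ln(2.333) = 0.847. Control rates other than 50% are assumptions, shown for range.

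| Control rate | Lower-titre rate | Odds ratio | Log OR |
|---|---|---|---|
| 30% | 10% | 3.86 | 1.350 |
| 40% | 20% | 2.67 | 0.981 |
| 50% (planned) | 30% | 2.33 | 0.847 |
| 60% | 40% | 2.25 | 0.811 |
| 70% | 50% | 2.33 | 0.847 |
| 80% | 60% | 2.67 | 0.981 |

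**Step 2: the reverse.** Fixing the log OR at 0.847 gives a difference of 14.5 points at a 30% control rate, 17.8 at 40%, 20.0 at 50%, 20.9 at 60% and 16.8 at 80%. For example, at 30% the odds are 0.4286/2.333 = 0.1837, so the rate is 0.1837/1.1837 = 0.155 and the difference 0.145. A margin converted at 50% would therefore be a different margin if the control rate came out elsewhere.

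**Step 3: one data set on both scales.** Assumed counts after dose 3: 60/120 (high) and 54/120 (low).

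- Contrast of βs: ln(60/60) − ln(54/66) = 0.201. SE = √(1/60 + 1/60 + 1/54 + 1/66) = 0.259. The 95% CI is −0.307 to 0.708.
- Rate difference: 0.500 − 0.450 = 5.0 points. SE = √(0.5×0.5/120 + 0.45×0.55/120) = 0.0644. The 95% CI is −7.6 to 17.6 points. Newcombe-Wilson gives −7.5 to 17.3.

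The second result can be judged directly: its upper bound is below 20. The first cannot.

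**Step 4: the difference is recoverable from the specified model.** The model has one parameter per dose-by-titre cell. The fitted rate is p = 1/(1 + e^−β), with delta-method SE p(1−p)·SE(β). For the high arm in step 3, this variance is 0.25² × (1/60 + 1/60) = 0.00208, equal to 0.5×0.5/120, so the back-transformation returns the difference and interval above. In a simulated trial (three arms, three doses, 120 per arm, exchangeable correlation, 66/120 versus 57/120 after dose 3) the logit contrast was 0.301 (−0.207 to 0.808). Back-transforming that fit gave 7.5 points (−5.1 to 20.1), and an identity-link GEE gave the same. In this borderline set the log-odds upper bound of 0.808 lies below 0.847, while the difference bound of 20.1 lies above 20, so the two scales can disagree on the conclusion.

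**The case against.** The best reply has three parts.

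1. **The GEE does not carry the decision.** SAP 7.1.4 and 9.1.2 bring it in as an addition. The 20% rule follows the Kaplan-Meier text and comes before the Newcombe-Wilson and GEE text. Both of those other analyses are on the difference scale. This stands, and it sets the weight of the point.
2. **The intention may be right already.** SAP 7.1.4 speaks of intervals for binomial proportions by Newcombe-Wilson and by GEE, which suggests that rates were meant. Table layouts sit in a separate templates document (SAP 20.1.13) that is not available here. This stands in part. It cannot be shown that the final table would hold log odds ratios, only that the model as written yields them and no stated step converts them.
3. **The model contains the answer.** Step 4 confirms this. The defect is an unstated output step, not an unsuitable model.

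Two stronger readings are tempting, and the documents support neither.

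- A reader might infer that the log-odds bound will be compared with 0.20, so that equal titres would usually fail. No sentence plans that comparison, and the SAP itself labels the contrast a log odds ratio.
- A reader might infer that the GEE, coded dose by dose, targets a different quantity from both other analyses, because an infant who responded and then waned would count as a non-responder after dose 3. Newcombe-Wilson is also worded as response after dose 3, and only Kaplan-Meier is explicitly cumulative. SAP 9.1.1 defines a responder across doses 1 to 3, and SAP 9.1.4 uses a cumulative title for a response tabulated at each time point. The ambiguity is general, not specific to the GEE, and the documents give no waning rate from which to size it.

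**Conclusion.** SAP 9.1.2 contradicts itself on the scale of the GEE contrast. Followed literally, the model gives results that are not the promised difference and cannot be set against the 20-point margin. The size of the mismatch depends on the control rate: 20 points is a log odds ratio of 0.85 at the planned 50%, 1.35 at 30% and 0.81 at 60%, so no fixed conversion repairs it. This is algebra and needs no assumption beyond the range of control rates shown. The counts of 60 and 54 out of 120 and the simulated set are illustrations only.

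The SAP should be corrected before analysis, but the primary conclusion is not at risk from this point. The firm finding is the clash between the promised difference and the stated log odds ratio. The clash with the margin applies to the extent that the GEE is used to judge non-inferiority, as its place under that heading implies. Separately, the SAP leaves open whether the dose-3 outcome is cumulative, for Newcombe-Wilson as much as for the GEE.

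**What to change.** Amend SAP 9.1.2 as follows.

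1. Keep the GEE with one parameter per dose-by-titre cell. State that the dose-3 cell probabilities are back-transformed, and that high minus mid and high minus low are reported as risk differences with delta-method 95% intervals. An identity link is an acceptable alternative. With incomplete visits it does not guarantee fitted values between 0 and 1, so back-transformation is the safer default.
2. State whether the GEE risk difference is judged against 20% or is descriptive. Label any odds ratio as supplementary and not compared with 20%.
3. State one outcome coding for both the Newcombe-Wilson and GEE analyses: either cumulative, as in the primary objective (Protocol 4.1, SAP 2.1.1), or response at the sample after dose 3. Recoding only one of them would create a new mismatch.
4. Apply the same wording to vaccine take and its components, and name one SAS procedure for the model, since the text now names both PROC GEE and PROC GENMOD.

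The cost is SAP wording and a few lines of code, with no new data and no change to the design or sample size.

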9.1.3 Serum IgA

Serum IgA titres will be summarised at each serum collection time point, by treatment group using geometric means and the mean and standard deviation on the log scale. Measurements below the lower limit of detection will be assigned a value of half of limit for analysis e.g., if IgA is <20, this will be assigned a value of 10. This will be performed by the laboratory personnel prior to data transfer. The number of participants (and proportion) with measurements below the lower limit of detection will also be presented, using frequency tabulations. Infant and neonatal Serum IgA titres will also be listed on log scale by treatment group on FAS population.

9.1.4 Cumulative serum Anti-Rotavirus IgA Response

The number and proportion of participants with a positive serum anti-IgA rotavirus response (defined as \geq 3 fold increase in titre from baseline in anti-rotavirus IgA, to post investigational product dosing) at each serum collection time point will be summarised, by treatment group for the neonatal vaccine schedule group and the infant vaccine schedule group, using frequency tabulations.

9.1.5 Cumulative Vaccine Take After Three Doses of RV3-BB

Baseline values of IgA measurement for the neonatal schedule will be obtained from analysis of cord blood. Baseline values of IgA measurements for the infant schedule will be obtained from analysis of sera collected prior to the second dose of investigational product.

Neonatal comparison - a positive cumulative vaccine take corresponds to a serum immune response post investigational product doses 1, 2 or 3 or detectable RV3-BB virus shedding in stool (days 3, 4 or 5) post investigational product doses 1, 2 or 3.

Infant comparison - a positive cumulative vaccine take corresponds to a serum immune response post investigational product doses 2, 3 or 4 or detectable RV3-BB virus shedding in stool (days 3, 4 or 5)) post investigational product doses 2, 3 or 4.

9.1.6 Cumulative Vaccine Take After Two RV3-BB Doses

The number and proportion of participants with cumulative vaccine take after two RV3-BB doses (i.e., infant schedule with positive serum immune response post investigational product dose 2 or 3 or RV3-BB virus shedding in stool post investigational product dose 2 or 3 or neonatal schedule with positive serum immune response post investigational product dose 1 or 2 or RV3-BB virus shedding in stool post investigational product dose 1 or 2) will be summarised, by treatment group for the neonatal and infant schedule groups, using frequency tabulations.

9.1.7 Cumulative Vaccine Take After one RV3-BB Doses

The number and proportion of participants with cumulative vaccine take after the first RV3-BB dose (i.e., neonatal schedule with positive serum immune response post investigational product dose 1 or RV3-BB virus shedding in stool post investigational product dose 1 compared to "placebo" infant schedule with positive serum immune response post investigational product dose 1 or RV3-BB virus shedding in stool post investigational product dose 1 or RV3-BB virus shedding in stool post investigational product dose 1 or RV3-BB virus shedding in stool post investigational product dose 1 or RV3-BB virus shedding in stool post investigational product dose 1 or RV3-BB virus shedding in stool post investigational product dose 1 will be summarised, by treatment group for the neonatal schedule group and the "placebo" infant group, using frequency tabulations.

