4.2 Secondary Objectives

The secondary objectives of the study are;

- To assess the cumulative anti-rotavirus serum IgA response (defined as a ≥3 fold increase from baseline) 4 weeks after 3 doses of RV3-BB administered in an infant schedule at a vaccine titre of 1 x 10⁷.
- To assess cumulative vaccine take and components of vaccine take after 3 doses of RV3-BB (titre of 1 x 10⁷) administered in a neonatal schedule versus three doses of RV3-BB in an infant schedule at a vaccine titre of 1 x 10⁷.
- To assess cumulative vaccine take and the components of RV3-BB vaccine take after 3 doses of RV3-BB administered as a neonatal schedule at a vaccine titre of 1 x 10⁷, 3 x 10⁶ or 1 x 10⁶.

To assess cumulative vaccine take and the components of vaccine take after 2 doses of RV3-BB administered as a neonatal schedule at a vaccine titre of 1×10^7 , 3×10^6 or 1×10^6 or 2 doses in the infant schedule at a vaccine titre of 1×10^7 .

- To assess cumulative vaccine take and components of vaccine take after the first dose of RV3-BB administered as a neonatal schedule at a vaccine titre of 1 x 10⁷, 3 x 10⁶ or 1 x 10⁶ compared to placebo (1st dose of IP in the infant schedule).
- To assess cumulative vaccine take and components of vaccine take after the first dose of RV3-BB at a vaccine titre of 1 x 10⁷, 3 x 10⁶ or 1 x 10⁶ in the neonatal schedule compared with the first dose of RV3-BB at a vaccine titre of 1 x 10⁷ in the infant schedule.
- To describe the geometric mean titre of the anti-rotavirus serum IgA response after 3 doses of RV3-BB administered as a neonatal or an infant schedule
- To describe the safety and tolerability of RV3-BB when administered as an infant or as a neonatal schedule.
- To describe the occurrence of diarrhea episodes in participants, according to severity and detection of wild-type rotavirus.

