10.5 Doses and treatment regimens

Approximately 688 participants will be prospectively randomised to one of the following four treatment groups in a 1:1:1:1 ratio.

- High dose neonatal RV3-BB vaccine schedule (1x10⁷titre dose). RV3-BB Vaccine for doses 1, 2 and 3 and placebo for dose 4
- Mid dose neonatal RV3-BB vaccine schedule (3x10⁶titre dose). RV3-BB Vaccine for doses 1, 2 and 3 and placebo for dose 4.
- Low dose neonatal RV3-BB vaccine schedule (1x10⁶titre dose). RV3-BB Vaccine for doses 1, 2 and 3 and placebo for dose 4.
- High dose Infant RV3-BB vaccine schedule (1x10⁷titre dose). Placebo for dose 1 and RV3-BB Vaccine for doses 2, 3 and 4

Participants will also receive a dose of commercially available Rotarix® at 18 weeks of age.

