2.1.2 Secondary objectives

The secondary objectives of this study are:

- To assess the cumulative anti-rotavirus serum IgA response (defined as a ≥3-fold increase from baseline) 4 weeks after 3 doses of RV3-BB administered in an infant schedule at a vaccine titre of 1x10⁷.
- To assess cumulative vaccine take and components of vaccine take after 3 doses of RV3-BB (titre of 1x10⁷) administered in a neonatal schedule versus three doses of RV3-BB in an infant schedule at a vaccine titre of 1x10⁷.
- To assess cumulative vaccine take and the components of RV3-BB vaccine take after 3 doses of RV3-BB administered as a neonatal schedule at a vaccine titre of 1x10⁷, 3x10⁶ or 1x10⁶.
- To assess cumulative vaccine take and components of vaccine take after 2 doses of RV3-BB administered as a neonatal schedule at a vaccine titre of 1x10⁷, 3x10⁶ or 1x10⁶ or 2 doses as an infant schedule at a vaccine titre of 1x10⁷.
- To assess cumulative vaccine take and components of vaccine take after the first dose of RV3-BB administered as a neonatal schedule at a vaccine titre of 1x10⁷, 3x10⁶ or 1x10⁶ compared to placebo (1st dose of IP in the infant schedule).
- To assess cumulative vaccine take and components of vaccine take after the first dose of RV3-BB at a vaccine titre of 1x10⁷, 3x10⁶ or 1x10⁶ in the neonatal schedule compared with the first dose of RV3-BB at a vaccine titre of 1x10⁷ in the infant schedule.
- To describe the geometric mean titre of the anti-rotavirus serum IgA response after 3 doses of RV3-BB administered as a neonatal schedule or an infant schedule.

- To describe the safety and tolerability of RV3-BB when administered as an infant or as a neonatal schedule.
- To describe the occurrence of diarrhoea episodes in participants, according to severity and detection of wild-type rotavirus.

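### SAP 9.1.7 covers first-dose vaccine take against placebo only; the separate objective comparing first RV3-BB doses between schedules has no composite take analysis in the SAP

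*SAP*

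**What the plan says.** SAP 2.1.2 and Protocol 4.2 give two distinct objectives for vaccine take and its components after the first dose. One sets each neonatal titre against the infant arm's placebo: "compared to placebo (1st dose of IP in the infant schedule". The other sets each neonatal titre against the infant arm's first active dose; in the protocol's words, "in the neonatal schedule compared with the first dose of RV3-BB at a vaccine titre of" 1 x 10⁷ in the infant schedule.

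Protocol 10.5 fixes which dose that is. The infant arm receives "Placebo for dose 1 and RV3-BB Vaccine for doses 2, 3 and 4", so its first RV3-BB dose is IP dose 2.

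The SAP then has three sections on cumulative take:

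- 9.1.5, after three RV3-BB doses. For the infant comparison, "a positive cumulative vaccine take corresponds to a serum immune response post investigational product doses 2, 3 or 4", or shedding after those doses.
- 9.1.6, after two RV3-BB doses: "infant schedule with positive serum immune response post investigational product dose 2 or 3", or shedding after those doses.
- 9.1.7, after one RV3-BB dose: "infant schedule with positive serum immune response post investigational product dose 1", or shedding after that dose. Its closing clause tabulates the neonatal group and an infant group that it labels as placebo.

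**The concern.** Sections 9.1.5 and 9.1.6 shift the infant arm by one IP dose, so that schedules are aligned on the number of RV3-BB doses received. Section 9.1.7 does not shift it. That is right for the placebo objective. But no section covers the objective that compares first RV3-BB doses between schedules, and SAP section 5 does not list it among the objectives moved elsewhere (only microbiome and immune-development work is moved).

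At stake is whether a birth dose takes as well as a first dose at 6 weeks, asked at each of three titres. If the SAP leaves the infant baseline, blood sample and stool window for that contrast undefined, a later analysis of it would have to be defined post hoc.

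**Working it through.** The plan states no figure for this point, so the check maps each vaccine-take objective in SAP 2.1.2 to the section and IP doses that serve it.

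| Objective | Neonatal IP doses | Infant IP doses | SAP section |
|---|---|---|---|
| After three RV3-BB doses | 1–3 | 2–4 | 9.1.5 |
| After two RV3-BB doses | 1–2 | 2–3 | 9.1.6 |
| First RV3-BB dose versus placebo | 1 | 1 | 9.1.7 |
| First RV3-BB dose versus first RV3-BB dose | 1 | 2 | none |

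**Could another section supply the last row?**

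- SAP 9.1.5 and 9.1.6 pool infant IP dose 2 with later doses, so neither isolates it. The opening of SAP section 9 likewise classifies infant take over doses 2, 3 and 4 together.
- SAP 9.1.4 tabulates IgA response by arm at each serum time point, and 9.1.8 tabulates shedding by arm and dose number. Both components after infant IP dose 2 will therefore be visible. Take, however, is a per-participant either/or. If the marginal proportions are a (IgA response) and b (shedding), and both are known for everyone, take can lie anywhere from max(a, b) to min(1, a + b). With a = b = 50%, chosen only for illustration, that is 50% to 100%. Two marginal tables do not give the composite.
- The GEE model in SAP 9.1.2 is limited to neonatal-schedule participants, with contrasts after dose 3.
- SAP 7.1.4 and 9.1.2 say that take is analysed in the same way as the primary endpoint. The primary analysis compares titres, and neither sentence names a first-dose contrast between schedules.
- Protocol 13.3.2 defers the detail of secondary endpoints to the SAP.

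**Infant IgA baseline in the existing 9.1.7 table.** SAP 7.1.2 sets the infant-schedule baseline as the serum taken before IP dose 2. That serum is also the only post-dose-1 sample. The fold change is then x / x = 1, below the threshold of 3, so an infant IgA response after placebo cannot occur. The fallback to cord or Visit 1 blood applies only when the post-dose-1 sample is missing, and then there is nothing to compare. The opening of SAP section 9 ties cord blood to the neonatal comparison, which might be meant to cover this table, but the SAP does not say so.

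**Sampling interval for the missing contrast.** Neonatal dose 1 is given at 0 to 144 hours (6 days) of age, and the next blood is at Visit 3, week 6 with +7 days (42 to 49 days of age). The interval is 42 − 6 = 36 to 49 − 0 = 49 days. Infant IP dose 2 is given at Visit 3, and the next blood is at Visit 5, week 10 ± 7 days (63 to 77 days) and at least 21 days later. The interval is 21 to 77 − 42 = 35 days. This assumes weeks are counted by age; bloods may be drawn up to 2 days before dosing. Nominally it is about 6 weeks against about 4.

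**The case against.** The best case on the other side has four parts.

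1. *The objective is not wholly unserved.* It covers take and its components, and both components are tabulated for the infant arm after IP dose 2. SAP 9.1.1 also defines cumulative take at the current assessment time point, and Kaplan-Meier estimates are promised for each vaccine arm. This stands in part: a reader might infer that nothing about the infant arm's first RV3-BB dose is reported, and that would be wrong. The composite and the contrast are still unspecified.
2. *Readers will not be misled.* One might infer from the heading of 9.1.7 that its table would pass for schedule against schedule. The text does not support that, because it labels the infant group as placebo twice. Only the heading is loose.
3. *The table may exist elsewhere.* SAP 20.1.13 refers to a separate templates document, which is not available here. The text of 9.1.7 also repeats a clause and leaves a bracket open, possibly an extraction or copying fault. A dropped clause cannot be excluded, but every legible infant clause refers to dose 1, and a table template does not replace a definition in the SAP.
4. *The importance is limited.* The second question in Protocol 3.9 concerns immune response by schedule, and the two-dose and three-dose sections address it. This stands: first-dose take is a supporting secondary objective.

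**Conclusion.** The gap is real and narrow. Followed as written, the SAP does not produce composite vaccine take after the infant arm's first RV3-BB dose, nor its comparison with neonatal dose 1. That is one of the nine secondary objectives in SAP 2.1.2, with three titre contrasts. The primary analysis is unaffected.

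No loss of power or precision can be assigned to the omission. An interval width could be calculated for the missing table, but it would rest on an assumed take rate and number evaluable, and it would not measure the effect of leaving the table out.

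The conclusion assumes that 9.1.7 as extracted has not lost a clause about infant IP dose 2. It is a point that should be corrected, at small cost.

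**What to change.** Split SAP 9.1.7 into two tables.

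**(a) After IP dose 1, RV3-BB versus placebo.** This is the present table, relabelled. State that cord or Visit 1 blood is the infant IgA baseline here, because the default pre-dose-2 serum is itself the post-dose-1 sample. A new label alone would leave that problem in place.

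**(b) After the first RV3-BB dose.** Compare each neonatal arm after IP dose 1 (cord baseline) with the infant arm after IP dose 2. Define infant take as an IgA response in the Visit 5 blood against the pre-dose-2 serum, or RV3-BB shedding on days 3–5 after IP dose 2. Report IgA response, shedding and take, with a Newcombe-Wilson 95% interval for each difference. State that interval explicitly for this contrast, since SAP 9.1.2 specifies it for IgA response after dose 3 and extends it to take only by a general sentence. Add a footnote that the IgA sample falls about 6 weeks after the neonatal dose and about 4 weeks after the infant dose.

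If table (b) already exists in the output templates, bring its definition into the SAP. The cost is SAP wording and one additional table; no new data are needed.
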